Screening: FMRI portion of the study explained to subject, including the cystometry and fMRI procedures. Subject administered OAB Awareness tool and fMRI eligibility assessed. Subject given voiding diary instructions. Subject given copy of consent and either has visit scheduled to sign consent after subject has time to consider whether she wants to participate in the study. If subject states she is certain that she wants to participate, she has the option of signing the consent at this time. If the consent is signed, then the subject is administered the medical history and demographic forms. If subject states at this visit that she would like to participate in the study, appointments are scheduled for the cystometry and fMRI and arrangements are made for the patient to receive prophylactic antibiotics prior to the bladder catheterizations. If patient is uncertain whether she wants to participate, the research coordinator's contact information is given to the subject.

Visit 1: Subjects return for the visit with the voiding diary and study eligibility is re-confirmed. The consent is signed, if this has not happened previously. The medical history and demographics forms are administered. POP-Q exam is performed if it has not been performed in the last year. Cystometry is explained to the subject once more. Urine pregnancy test is performed (if patient is premenopausal and has not had a hysterectomy or permanent sterilization procedure) and urine screen for UTI performed. Cystometry is performed as previously described in Visit #2 for the UUI subjects. The subjects will also have simulation of the procedure to be performed in the fMRI. Patients will have urine and vaginal swab samples collected and stored for possible future analysis (For example, urine may be analyzed for biomarkers and microbiome analysis). Future fMRI appointment is confirmed.

Visit 2: Urine pregnancy test performed (if patient is premenopausal and has not had hysterectomy or permanent sterilization procedure) and urine screen for UTI performed. FMRI procedures again explained to subjects. FMRI performed as described previously in visit 3 for fMRI UUI subjects. Subjects are given instructions and contact numbers to call in the event questions or problems arise. Subjects thanked and subject incentives given or arrangements made to give incentives.

Flow Diagram 1--- for UUI Subjects:

Screening Visit: Study explained to patient. Pt. administered OAB Awareness Tool & given voiding diary instructions. Pt. given copy of consent and either has visit scheduled to sign consent or pt. given research coordinator's info. for future contact

Study Visit #1: Pt returns for study visit with her voiding diary and voiding diary reviewed for study eligibility/UUI frequency. Consent Signed. fMRI eligibility assessed. Past medical history & Demographics sheet & baseline questionnaires (OAB-qSF, ISI,PBBC, PISQ-12, IBS Module, CRADI-8, BPIC and vas pain questionnaire administered). POP-Q exam performed if not performed in last 12 months. Cystometrics scheduled. FMRI may be scheduled (for fMRI eligible & willing subjects) @ this visit or arrangements made to contact subjects regarding fMRI. Arrangements made to contact pts for scheduling future appts. and for patients to receive prophylactic antibiotics for catheterization(s). Behavioral Therapy reviewed & handouts given

Study Visit #2: Cystometry explained to subject. Urine pregnancy test and urine screen for UTI performed. Cystometry performed. FMRI patients will undergo fMRI task simulation and have urine and vaginal swab samples collected and stored for possible future analysis. Subjects may undergo hypnotic susceptibility testing at this time or any time prior to initiating study treatment.

Study Visit #3: FMRI (up to 80) Urine screen for UTI and pregnancy test performed. FMRI procedures again explained to subjects. FMRI performed. Subject incentives given or arrangements made to give incentives.

Patients Randomized (N=152). Patients notified of randomization and of pending appointment times and dates Pretreatment Expectation question administered

 $\sqrt{}$ Study Visits #3-10 (or #4-11): 8 hypnotherapy sessions Study Visits #3-10 (or #4-11): 8 Pharmacotherapy sessions over 2 months. CD logs documenting home practice over 2 months. Medication logs gathered weekly and sent gathered weekly/sent to coordinator. Session(s) taped to study coordinator. Session(s) taped for quality for quality assurance and randomly audited. assurance and randomly audited. Study Visit #12: (for pts who had a Study Visit #12: (for pts who had a baseline fMRI & same procedure baseline fMRI & same procedure as as Visit #3): F/U fMRI performed Visit #3) F/U fMRI performed and and have urine and vaginal swab have urine and vaginal swab samples samples collected and stored for collected and stored for possible possible future analysis. future analysis.

Study Visit #11 (or #13): Final Research Coordinator Meeting with patients after treatment finished (approx. 2-3 months after randomization); f/u questionnaires administered (OABq-SF,ISI, PBBC, PISQ-12, CRADI-8,IBS Module, BPIC questionnaire, Post-treatment Expectation question), voiding diary and treatment compliance information collected. Urine may be collected and stored for possible future analysis. Plans for f/u explained & Contact information re-confirmed. Pt incentives given

6 mo. f/u with patients after treatment finished (approx. 6 months after treatment & may be phone/mail f/u): f/u questionnaires administered (OABq-SF, ISI,PPBC, PISQ-12, CRADI-8, IBS Module, BPIC, Post-treatment Expectation), voiding diary and treatment compliance information collected. Plans for f/u explained & Pt incentives given/mailed. Arrangements made for hypnotherapy patients who choose optional additional hypnotherapy session prior to 12-mo follow-up.

12 mo. f/u with patients after tx finished (approx. 12 months after tx & may be phone f/u): f/u questionnaires administered (OABq-SF, ISI,PPBC, PISQ-12, CRADI-8,IBS Module, BPIC, Post treatment Expectation question), voiding diary and treatment compliance information collected. Pts thanked and Pt incentives given/mailed

Flow Diagram 2--- for fMRI Normative Controls:

Screening Visit (subject may also sign consent at this visit if desired): FMRI Study explained to subject. Subject administered OAB Awareness Tool and fMRI eligibility assessed. Subject given voiding diary instructions. Subject given copy of consent and either has visit scheduled to sign consent or if subject wishes, may sign consent at this time. If consent has been signed at this visit, the Past Medical History and Demographic forms will be administered at this time. Cystometry and fMRI procedures will be explained to the subject. Appointments for subject to undergo cystometry (see visit 1) & fMRI may be scheduled at this time or subject may be given research coordinator's info. for future contact. Arrangements made for patient to receive prophylactic antibiotics prior to bladder catheterizations.

Study Visit #1 Cystometrics: Subjects (up to 30-35) return for study visit with voiding diary and study eligibility (for FMRI as a normal control) confirmed. Consent signed if this has not happened previously and past medical history/Demographics sheet administered if consent signed at this visit. POP-Q exam performed if not performed in last year. Cystometry explained to subject. Urine pregnancy test and urine screen for UTI performed and have urine and vaginal swab samples collected and stored for future analysis. Cystometry and fMRI task performed. fMRI appointment confirmed.

Study Visit #2 fMRI: Urine screen for UTI and pregnancy test repeated. FMRI procedures again explained to subjects. FMRI performed. Subjects are given instructions and contact numbers to call in the event questions or problems arise. Subjects thanked and subject incentives given or arrangements made to give incentives.

4. Selection and Enrollment of Participants

4.1 Inclusion Criteria & 4.2 Exclusion Criteria:

All study participants must meet all the inclusion criteria as noted below to participate in the study. Additionally, if subjects have any of the exclusion criteria as specified below, they will be excluded from the respective portion of the study.

For the RCT:

Inclusion Criteria for the RCT: Women with Urgency Urinary Incontinence (UUI) who meet inclusion criteria and who choose to participate in the study will be enrolled. They must be able to understand the study procedures and agree to comply with them for the duration of the study. Inclusion criteria:

- Non-pregnant English-speaking women
- > 18 yo
- OAB Awareness scores ≥ 8
- \geq 3 UUI episodes/week for \geq 3 months

Exclusion Criteria for the RCT: Women who have any of the exclusion criteria as specified below will be excluded from study participation

- Women with a history of neurologic diseases such as Multiple Sclerosis, Parkinson's disease, stroke, or dementia
- History of schizophrenia or untreated bipolar disorder or current drug or alcohol dependence
- Women who have taken anticholinergic medications for UUI within the last 3 weeks (women who have taken anti-cholinergics for UUI but discontinued them > than 3 weeks ago may participate in the study) or have a sacral neuromodulator in place to treat UUI or have received Onabotulinum toxin A in the last 12 months to treat UUI
- Contraindications to anticholinergic medications (untreated narrow angle glaucoma, significant urinary retention or gastric retention)
- Pregnant women or lactating women, women who plan to become pregnant in the next year, or premenopausal women unwilling to use contraception if engaging in sexual relations during the year of study participation (hysterectomy is considered to be a form of contraception)
- Untreated urinary tract infection
- Prolapse which extends past the hymen (POP-Q points of ≥ 1+) which may be responsible for UUI symptoms
- Women who cannot keep the majority of the study therapy appointments or those without reliable contact phone numbers or methods of communication with the study personnel.

For the fMRI:

Inclusion Criteria for UUI subjects participating in the fMRI portion of the study: Women with UUI who meet criteria for the RCT and who are willing to participate in the fMRI portion of the study. They must be able to understand the study procedures and agree to comply with them.

Exclusion Criteria for UUI subjects participating in the fMRI portion of the study: Women who have any of the exclusion criteria as specified below will be excluded from participation in the fMRI portion of the study

• Women with a history of severe claustrophobia or ferro-magnetic implants such as cochlear implants, cardiac pacemakers or aneurysm clips.

Inclusion Criteria for normative controls participating in the fMRI study: These women must be able to understand the study procedures and agree to comply with them. Other criteria:

- Women 46-80 years old*
- Absence of UUI/OAB symptoms or treatment
- OAB Awareness Tools Scores <8
- Willingness to undergo fMRI

*Explanation of age range for the above: In an attempt to assure comparable age ranges of controls to affected UUI subjects, we initially pooled data from both our pilot hypnotherapy and pilot fMRI studies and have found that the median patient age was 54 with the second quartile=46-54, and third quartile=55-62. We initially chose these quartiles as the age range for the normative control group but subsequently found that the age range was overly restrictive in the upper age ranges. We expanded the upper limit to 80 years in order to have flexibility in age adjustment of controls.

Exclusion Criteria for normative controls participating in the fMRI study: Women who have any of the exclusion criteria as specified below will be excluded from participation in the fMRI portion of the study

- Women with UUI/OAB
- Women with a history of neurologic diseases such as Multiple Sclerosis, Parkinson's disease, stroke, or dementia
- History of schizophrenia or untreated bipolar disorder or current drug or alcohol dependence
- Pregnant women or lactating women, women who plan to become pregnant in the next year, or premenopausal women unwilling to use contraception if engaging in sexual relations during the year of study participation (hysterectomy is considered to be a form of contraception)
- Untreated urinary tract infection
- Women with a history of severe claustrophobia or women with ferro-magnetic implants such as cochlear implants, cardiac pacemakers or aneurysm clips

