
Hypnotherapy offers a mechanism to sustain that effect in order to provide clinically useful therapy. The hypnotic state results in functional changes in the limbic cortex. It has been shown to decrease anterior cingulate cortex activation in response to acute pain and in response to conflict monitoring.^{63,73} The interaction between the anterior cingulate cortex and the other portions of the brain during hypnosis, however, is not constant across all settings. Connectivity with the prefrontal and frontal cortex may increase when pain is suppressed by hypnosis and diminish when conflict monitoring is suppressed by hypnosis.^{24,25,53,60} Furthermore, the anterior cingulate cortex is not the sole target in the limbic cortex for mind/body therapies. It appears to be an important nexus for acute stimuli but chronic symptoms may be mediated elsewhere.³¹ Treatment of chronic pain with both hypnosis and acupuncture is associated more strongly with decreased activation of the insula and alterations of its connectivity to other sites including the central executive network.^{2,5,48} Modulation of activity in these sites has been associated with acute amelioration of chronic pain.⁶⁹ Alteration of insula connectivity persists for the first hour following therapy and may be important in achieving a sustained treatment effect.

Our working hypothesis is that among patients with urgency incontinence hypnotherapy causes sustained decreases in abnormal evoked activation of the limbic cortex in response to bladder distension and/or modulates abnormal intrinsic activity (functional connectivity) in these same areas. We also predict that this normalization of evoked activation and functional connectivity will be greater than that seen with

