
Visit 12—follow-up fMRI testing (for the fMRI group): Follow-up fMRI will be performed on the subjects who had baseline fMRIs performed. These will be performed in the same fashion as described in Visit #3. In addition, patients may have urine and vaginal swab samples collected and stored for possible future analysis (For example, urine may be analyzed for biomarkers).

Final visit 11 (for those who did not undergo fMRIs) and Final visit 13 (for those who did undergo fMRI): The final study visit will be scheduled at the end of the hypnotherapy or medication counseling sessions, approximately 8-12 weeks after study entry. Those who are in the subgroup who have undergone prior fMRI testing will have it performed at this session. At the final study visit, subjects will 1) be administered the OABq-SF, ISI, the PPBC, CRADI-8, IBS Module and IC questionnaires, PISQ-12 and answer the question regarding

how well the therapy met their expectations for treatment. Their compliance with medications or home practice of hypnotherapy will be documented 2) They will return their follow-up voiding diary 3) receive patient incentives for the time and inconvenience they have experienced from study participation. In addition, patients may have urine and vaginal swab samples collected and stored for possible future analysis (For example, urine may be analyzed for biomarkers).

Length of visits: Each hypnotherapy session will last approximately 60 minutes, each pharmacotherapy visit will take approximately 20-60 minutes, and each Brain fMRI visit will last approximately 60-120 minutes. The 6 and 12 month visits may be conducted via phone or mail, if the subject desires, in order to decrease subject inconvenience.

B. NORMATIVE CONTROLS PARTICIPATING IN ONLY THE FMRI STUDY:

In addition to the UUI study subjects described previously, we will also enroll a group of women without UUI and OAB symptoms (and with OAB Awareness Tool screening questionnaire scores < 8). This normative group (approximately 30-35 subjects) will keep voiding diaries, answer questionnaires, and undergo urine pregnancy and dipstick testing and cystometric testing and receive prophylactic antibiotics (as described previously) followed by performance of a Brain MRI in order to compare baseline fMRIs in women with and without UUI.

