Hypnotherapy: Hypnotherapy will be administered over 8 weeks in 8 sessions by certified, trained clinical hypnotherapists in their outpatient offices. The subjects will be informed that several or all sessions will be audiorecorded and one or more sessions will be reviewed by study personnel to ensure that the hypnotherapist administers the hypnotherapy session in a standardized fashion. Recordings will be stored on the research computer and access to these recordings will be available to assigned research personnel only. All recordings will be stored for approximately 7 years, in the same fashion as other data, and then will be destroyed. The hypnotherapists have been instructed to not use the patients' name or any other identifiers during the recorded session. Sessions will last approximately 1 hour with a brief outline of these sessions as follows; Session #1: The hypnotherapist will explain hypnotherapeutic principles; subjects will inform the hypnotherapist regarding any phobias or fears (so that these triggers will be avoided). Subjects will undergo their 1st hypnotherapy session and hypnosis will then be terminated. Session #2: address emotions around OAB and life impact, visualize pelvic floor exercise mechanics, and undergo their 2nd hypnotherapy session followed by termination of hypnosis. Subjects may choose to either receive a CD or to download a digital recording (for use on a digital device) specially prepared for them to for home practice of hypnotherapy sessions. This will occur at either their 2nd or 3rd hypnotherapy session; they will be instructed NOT to listen to the hypnotherapy CD/digital recording while driving and encouraged to listen to the CD/digital recording daily and record the home use of their CD/digital recording. Session #3,4,5,6,7; same as session 3. Session #8: same as previous sessions. In addition, the subjects will be counseled to expect occasional and temporary setbacks in their bladder symptoms and the hypnotherapist and subject will discuss how to cope with these setbacks. The details of these sessions are detailed in the "Hypnotherapy Session Guidelines" (see Attached MOP). Following the 8 weeks of therapy, subjects will be encouraged to continue to practice self-hypnosis and/or listen to their home practice CD/digital recording given to them and this practice will be tracked for the 1 year duration of the study. Hypnotherapy patients will also have the opportunity to have one additional hypnotherapy session prior to their 12-month followup visit: arrangements for the session can be initiated at their 6-month follow-up visit.

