Cystometrics (Day -60 to -1) Cystometric testing (a bladder filling test during which patient sensations are recorded at various volumes and evidence of stress or urgency incontinence recorded) will be performed. Testing includes a urine pregnancy test and urine dipstick. See MOP Chapter "Study Procedures" regarding forms to be filled. If subject chooses to undergo an fMRI, they will have simulation of their fMRI task performed and may have urine and vaginal swab samples collected and stored for possible future analysis (For example, urine may be analyzed for biomarkers and microbiome analysis. See MOP Chapter "Study Procedures" regarding forms to be filled as noted in Section 5.1.

Baseline FMRI

FMRI (Day -60 to -1 for baseline and week 9 for follow-up) will be performed on women willing and able to have fMRI at baseline and follow-up. Testing includes a urine pregnancy test and urine dipstick. Forms to be completed include the fMRI procedure are noted in the "Study Procedures" MOP and has been described in the Protocol Section 5.1.

Other Baseline Tests/Questionnaires

Stanford Hypnotic Susceptibility Testing (Day -60 to week 1) this validated test may be administered by the hypnotherapist any time before the subject receives either their pharmacotherapy or hypnotherapy intervention. Its administration depends primarily on scheduling issues between the subject and hypnotherapist; attempts will be made to couple this testing with any of the subjects' pre-treatment visits (enrollment, cystometrics, fMRI) though the subject may have to come for a separate visit if this is not possible.

Patient Expectation Question (Day 0 and prior to treatment) the subject will be administered this question after randomization and prior to treatment. The question will be explained to the patient at enrollment, but will not be administered until the patient is notified regarding her group assignment by the Research Coordinator or her designee.

Randomization

Randomization to Treatment (Day 0) Subjects will be informed of their randomization to treatment by the Research Coordinator (or her designee if she is absent). Please refer to Statistics Section 9. Randomization will occur within 2-months of Enrollment. Treatment visits will be initiated within one month following randomization with a goal of initiating treatment within 1 week. However, subjects will be given the necessary time to prepare for their upcoming weekly treatment sessions.

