6.2.5 Follow-up Assessments

All subjects will have follow-up assessments irrespective whether they discontinue study interventions or are non-compliant with interventions or use off-protocol treatments.

Follow-up Assessment at End of Treatment (weeks 8-10 depending on whether subject had fMRI): A subject visit will be arranged by study personnel for the post-treatment (end of counseling/hypnotherapy session) assessments which should occur within 2 weeks of finishing the treatment sessions for those subjects not undergoing fMRI or within 3 weeks of finishing treatment for those who will also undergo a follow-up fMRI. Subjects may have urine and vaginal swab samples collected and stored for possible future analysis (For example, urine may be analyzed for biomarkers).

The assessments and visit will include

- Questionnaires; OABq-SF, ISI, PPBC, PISQ-12, CRADI-8, IBS Module, and IC questionnaire. Follow-up Expectation Question and Compliance Questionnaire
- Voiding Diary
- Subject feedback regarding study participation
- Confirm subject contact information (patient email address, mailing address, cell and landline phone numbers, name/address/phone number of friend or relative in event of difficulty contacting patient)
- Confirm arrangements for patient incentive payments and for follow-up in 6 months

6 month Follow-up (month 6) the Study Coordinator or her designee will arrange 6 month follow-up assessment visits for subjects. Although it is preferable to have an in-person visit, it is possible to have the visit performed via phone and mail. Patient reimbursements will be paid at the in-person visit. If the subject has a phone/mail visit arrangements for reimbursement will be made following completion of this visit. The follow-up assessment should be completed within 5-7 months of completion of hypnotherapy or pharmacotherapy sessions.

Final assessments & follow-up include

- Questionnaires; OABq-SF, ISI, PPBC, PISQ-12, CRADI-8, IBS Module and IC questionnaire. Follow-up Expectation Question and Compliance Questionnaire
- Voiding Diary
- Subject feedback regarding study participation
- Confirm subject contact information (patient email address, mailing address, cell and landline phone numbers, name/address/phone number of friend or relative in event of difficulty contacting patient)
- · Confirm arrangements for patient reimbursement and for follow-up at 12 months

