Statistical Analysis 2.2 Pre- and Post-Treatment measurements in patients with UUI: Prior functional MRI analysis during the hypnotic state has shown complete suppression of anterior cingulate cortex activation in response to pain.⁵⁵ However, the magnitude of suppression of anterior cingulate cortex or insula signal outside the hypnotic state has not been studied. Current study size will be able to detect differences between pre and post treatment signal within a treatment group with an effect size of approximately 0.5 and a power of 0.8. Minimal effect size would be approximately equivalent to a 60% decrease in the excess (above normative control) anterior cingulate cortex and insula signal. We predict a main effect of time, suggesting that both treatments are effective in reducing activity within the anterior cingulate cortex and insula. However, we also predict a significant Group x Time interaction, indicating that that change in activity will be greater for the hypnotherapy relative to the pharmacotherapy group. Minimum detectable effect size for the Group X Time interaction is 0.7 with power of 0.8 and alpha of 0.05. Similar to brain activation, no prior data is available in the literature regarding the expected change in waking state connectivity following hypnotherapy. Current study size will be able to detect within-group differences between pre and post treatment signal with a minimal effect size of approximately 0.5 and a power

of 0.8, much lower than the observed effect size of >3 in our pilot study. The minimum effect size would be reached with a 15% decrement in anterior cingulate cortex to insula connectivity. As for evoked activity we predict both a main effect of time, and predict a significant Group x Time interaction, indicating that change in functional connectivity will be greater for the hypnotherapy relative to the pharmacotherapy group. Minimum detectable effect size for the Group X Time interaction is 0.7 with power of 0.8 and alpha of 0.05. This minimum effect size will be reached when between group differences in anterior cingulate cortex to insula connectivity are \geq 30%.

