Anticipated/Expected Outcomes: Results from this study should confirm the differences between normative and urgency incontinence subjects with respect to limbic system evoked activation and functional connectivity. Confirmation of abnormal functional connectivity in urgency incontinence subjects during the resting state would be a particularly important contribution to the study of functional disorders in general. Abnormal resting connectivity data does not require that data be acquired and temporally linked to a performance of a task while in the MRI scanner making data acquisition less technically demanding. Abnormal resting connectivity has thus far only been observed in fibromyalgia but if shown to be more widely present among functional disorders could prove a diagnostic tool and/or target of new therapies. Demonstration that hypnotherapy's impact on brain activation and connectivity extends past the hypnotic state and persists during wakefulness would allow treatment effects of hypnotherapy, and perhaps other mind/body therapies, to be assessed temporally distant from the time of therapy. The delayed assessment should give much better insight into the likelihood of a durable clinical benefit for the patient. Demonstration that hypnotherapy has greater impact on functional MRI findings than pharmacotherapy would argue that resultant brain plasticity is related to mind-body therapy rather than due to altered sensory input (from the bladder).

10. Data Collection and Quality Assurance

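### Nothing separates home self-hypnosis from the week 9 fMRI, so the Aim 2 conclusion of a brain effect outside hypnosis is unprotected, although the randomised comparison stands

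*Combined protocol and SAP*

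**What the plan says.** **The intended conclusion.** Section 2.2 sets out to show a lasting post-therapy change in limbic function that holds when the woman is not hypnotised. Section 9.6 (Anticipated/Expected Outcomes) says that showing that hypnotherapy's impact "extends past the hypnotic state and persists during wakefulness would allow treatment effects of hypnotherapy" to be assessed at a distance in time from therapy.

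**The scan.** Section 6.2.2 gives the timing: "FMRI (Day -60 to -1 for baseline and week 9 for follow-up) will be performed" on willing and able women. Section 3, Visit 12, describes the follow-up scans only by reference to the baseline procedure: "These will be performed in the same fashion as described in Visit #3". Under Section 5.1, Task A is continuous key-press rating of urge during bladder filling, and Task B is 10 minutes of fixation with no rating.

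**Home practice.** Sections 3 and 5.1 encourage daily use of the recording during treatment. After the eight weeks, "subjects will be encouraged to continue to practice self-hypnosis and/or listen to their home practice CD/digital recording given to them". In Table 1 (Section 6.1) the recording-use logs are ticked at treatment visits 1 to 8 and not at the week 9 scan.

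**What the plan says about acute effects.** Section 2.2: "Alteration of insula connectivity persists for the first hour following therapy and may be important in achieving a sustained treatment effect". Section 9.2: "Prior functional MRI analysis during the hypnotic state has shown complete suppression of anterior cingulate cortex activation in response to pain".

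**The concern.** The plan cites strong acute effects of hypnosis on the regions it will measure, and it wants to show something different: a change that remains when the woman is awake and not hypnotised. To tell the two apart, the scan has to be taken away from hypnosis, or at least the distance has to be known. As written, a hypnotherapy woman could use her recording on the morning of the scan, or use self-hypnosis during it, and no scheduled form would show this. The medication arm has no counterpart. A larger fall in anterior cingulate or insula signal, or a larger connectivity change, could then reflect an acute state or a short carry-over, and would point in the direction the trial predicts. Sections 9.2 and 9.6 call the study of mechanism the principal purpose of this analysis, so this distinction is central to Aim 2.

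**Working it through.** **1. Is there any separation?** I compared the descriptions of the scan and of home practice.

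| Item | Place | Content |
|---|---|---|
| Therapist sessions | 5.1; 6.2.4; Table 1 | Eight, weeks 1–8; hypnosis ended within the session |
| Follow-up scan | 6.2.2; Table 1 | Week 9, separate visit; no induction or recording |
| Scan procedure | 3 (Visits 3 and 12); 5.1 | Same as baseline; home practice not mentioned |
| Home practice | 3; 5.1 | Daily in treatment; encouraged afterwards |
| Practice logs | Table 1 | Treatment visits 1–8 only |
| Compliance questionnaire | 5.4; Table 1 | End-of-treatment visit, 6 and 12 months; analysed as yes/no and number of times practised |

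The scan is separated from therapist sessions. From home practice, the specified minimum interval is none. No item listed is time since last practice.

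**2. Scan timing is not stated consistently.** Section 3 lists Visit 12 as its own visit, then says of the final visit: "Those who are in the subgroup who have undergone prior fMRI testing will have it performed at this session". Section 6.2.5 allows the post-treatment assessment "within 3 weeks of finishing treatment for those who will also undergo a follow-up fMRI". Neither reading creates an interval from home practice.

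**3. Which outcome is most exposed?** Task A requires continuous responding, with eye-tracking. That makes a hypnotic state during filling less likely but does not exclude it, and it does nothing about carry-over from earlier that day. Task B is passive and feeds the connectivity outcome, which is the type of measure to which the cited one-hour carry-over applies.

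**4. The plan's own figure.** The précis plans up to 60 analysable UUI datasets, about 30 per arm. Section 9.2 gives a minimum detectable Group x Time effect of 0.7 at 80% power and two-sided alpha 0.05. With 30 per arm the detectable effect is (1.960 + 0.842) × √(2/30) = 0.72 by the normal approximation, or 0.74 by the t-test. This agrees with the stated 0.7 after rounding, so 30 per arm is a fair basis for step 5.

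**5. Illustration of size (activation only).**
- Section 9.2 equates an effect size of about 0.5 with a 60% fall in the excess signal, so the whole excess is 0.5 / 0.6 = 0.83 SD.
- Assumptions: no lasting effect in either arm; complete suppression of the excess in affected women, by analogy with the pain result cited in Section 9.2; the same SD of change in both arms; a share *s* of hypnotherapy women affected.
- Apparent Group x Time effect: d = *s* × 0.83. Noncentrality: d × √(30/2). Two-sided 5% two-sample t-test, 58 degrees of freedom.

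| Assumed share *s* | d (SD) | Noncentrality | Chance of p<0.05 |
|---|---|---|---|
| 0% | 0 | 0 | 5% |
| 25% | 0.21 | 0.81 | 12% |
| 50% | 0.42 | 1.61 | 35% |
| 75% | 0.63 | 2.42 | 66% |

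Allowing for the extra variance when only some women are affected lowers the last three figures by at most about 3 percentage points. If suppression were half rather than full, d would halve: a 50% share would then give 0.21 SD and about 12%. The documents give no basis for the same calculation on connectivity.

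**The case against.** **The primary outcome is not restricted to the waking state.** Sections 9.1 and 9.51 define it as the between-group difference in change following treatment. Home practice is part of assigned hypnotherapy, and Section 5.1 has the medication arm continuing its drug, so both arms are scanned on treatment. This stands. A reader might infer that the Group x Time contrast is biased. The documents do not support that for a comparison of assigned treatments; the weakness lies in the mechanistic reading.

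**The scan is not taken in hypnosis by design.** This also stands. A reader might infer that there is no separation at all, or that women are trained to use self-hypnosis when bladder filling provokes urge. The therapist sessions end before the scan, and the session outlines in Sections 3 and 5.1 do not describe such training. In-scanner use is a possibility that the plan leaves open, not one it prescribes.

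**The one-hour carry-over is loosely sourced.** The sentence in Section 2.2 follows text on both hypnosis and acupuncture, and presents the persistence as possibly useful. It shows that the plan recognises a short-lived effect, but it does not establish a wash-out time.

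**The information may exist elsewhere.** Section 5.1 says practice will be tracked for the year, and compliance is documented after the scan. The Manual of Procedures, the compliance form and the fMRI checklist are not among the documents and may hold an instruction or a time field. It cannot therefore be said that timing is certainly unrecoverable, only that the protocol does not schedule its collection.

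**The illustration stacks assumptions.** It carries a cingulate result for pain over to bladder-evoked cingulate and insula signal, and the shares are assumed. That is correct, and the figures should be read only as showing that the effect need not be trivial.

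**Conclusion.** The gap is real and bears on interpretation. The protocol sets no separation between home practice and the week 9 scan, gives no instruction about self-hypnosis in the scanner, and schedules no record of time since last practice. The randomised between-arm difference in change remains valid as a comparison of assigned treatments. What is unprotected is the stated conclusion that the effect lasts outside the hypnotic state and during wakefulness, most clearly for resting connectivity.

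It would go too far to say that this conclusion cannot be supported: the scan follows the therapist sessions, contains no induction, and Task A works against a hypnotic state. But a positive Aim 2 result could not be told apart from acute hypnosis or short carry-over using the data the protocol schedules, and this could not be reliably repaired afterwards. The size is unknown. The 12%, 35% and 66% figures depend on assumed shares, full suppression and no lasting effect. The conclusion also assumes that the unseen manual does not already deal with the matter.

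**What to change.** 1. **Scan-day practice.** In the Visit 12 procedure (Sections 3 and 5.1), ask that any home practice on the scan day be done after scanning.
2. **One script for both arms.** Before the tasks, read every woman the same instruction to do them in her ordinary waking state, without relaxation or self-hypnosis techniques. Identical wording keeps the script from revealing allocation.
3. **Record exposure away from the readers.** Have the study coordinator, who already knows the assignment (Section 6.2.2), record the date and time of last practice and any in-scanner use. Use a separate form rather than the fMRI task sheet, because those interpreting the scans must stay blinded (Sections 6.2.3 and 10.1).
4. **Supportive analysis.** In Section 9.6, add an Aim 2 sensitivity analysis by time since last practice, leaving out women who practised before the scan that day or in the scanner. Label it non-randomised, since it selects on behaviour after randomisation.
5. **Timing.** Reconcile the two statements in Section 3 on when the follow-up scan takes place.

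If items 1 to 3 are not adopted, limit the Aim 2 conclusion to change while on treatment.

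The cost is one home-practice session moved within the day, one short form and one extra analysis.
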